12 EFFICACY ANALYSIS

Unless otherwise noted, all efficacy analysis will be performed on the mITT analysis set. The per protocol analysis set will be used as supportive information for all efficacy analyses.

12.1 Primary Endpoint

12.1.1 Peak-Pruritus Numerical Rating Scale

The intensity of pruritus (itch) will be recorded daily in the eDiary from the screening visit until Day -1 and from Day 2 to the Day 29 visit, using the Peak-Pruritus Numerical Rating Scale (PP-NRS) (24-hour recall period). This NRS will be evaluated by asking participants to assign a numerical score representing their itch at the worst moment during the previous 24 hours on a scale of 0 to 10, with 0 being no itch and 10 being the worst itch imaginable.

The PP-NRS will be analyzed as follow:

- Change from baseline in PP-NRS at Day 2 (24-hour recall period after first application).

12.1.2 Primary Analysis

The primary endpoint, change in PP-NRS from baseline at Day 2 (24-hour recall period after first application), will be analyzed descriptively. The 95% CI will be provided for the mean change.

12.2 Secondary Endpoints

12.2.1 Modified Peak-Pruritus Numerical Rating Scale

On Day 1 only, participants will be asked to evaluate the current intensity of their itch at the time of assessment (ie, prior to the morning study drug application and 15, 30 minutes, 1, 2, 4, 6, and 12 hours after the morning study drug application; the 12-hour evaluation will occur prior to the second daily study drug application) on a scale from 0 to 10, with 0 indicating no itch and 10 indicating the worst imaginable itch. The modified Peak-Pruritus Numerical Rating Scale (mPP-NRS) (current itch intensity) was modified from the PP-NRS.

The mPP-NRS will be analyzed as follow:

	STATISTICAL ANALYSIS PLAN, Version Final v1.0
Protocol Number: INCB 18424-901	Sponsor: Incyte Corporation
Study Title: An Open-Label, Single-Arm Study to Evaluate the Effect of Ruxolitinib 1.5% Cream on Itch in Adult Participants With Atopic Dermatitis (SCRATCH-AD)	

- Change from baseline in mPP-NRS (current itch intensity) at 15 and 30 minutes and 1, 2, 4, 6, and 12 hours postdose on Day 1.
- Proportion of participants achieving at least a 1-grade decrease from baseline in mPP-NRS at 15 and 30 minutes and 1, 2, 4, 6, and 12 hours postdose on Day 1.
- Proportion of participants achieving at least a 2-grade decrease from baseline in mPP-NRS at 15 and 30 minutes and 1, 2, 4, 6, and 12 hours postdose on Day 1.

12.2.2 Peak-Pruritus Numerical Rating Scale

The PP-NRS is defined in section 12.1.1. The PP-NRS will be analyzed as follow:

- Change from baseline in PP-NRS from Day 3 through Day 29.
- Proportion of participants achieving at least a 1-grade decrease from baseline in PP-NRS from Day 2 through Day 29.
- Proportion of participants achieving at least a 2-grade decrease from baseline in PP-NRS from Day 2 through Day 29.

12.2.3 Minimal Clinically Important Difference

The minimal clinically important difference (MCID) corresponds to an achievement of ≥ 2 -grade reduction in PP-NRS and mPP-NRS from baseline.

The MCID will be analyzed as follow:

- Time to MCID for PP-NRS (≥ 2 -grade reduction in PP-NRS from baseline).
- Time to MCID for mPP-NRS (≥ 2 -grade reduction in mPP-NRS from baseline).

The time to MCID will be defined as the time from the date (time) of first dose to the date (time) of first occurrence of MCID. The time to MCID for the PP-NRS will be reported in days, and the time to MCID for the mPP-NRS will be reported in hours.

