2.2.1. Scientific Rationale for Study Design

During the study, all participants will apply ruxolitinib 1.5% cream on all AD lesions for 28 (± 2) days. The proposed design is considered appropriate to evaluate the onset of itch reduction following application of ruxolitinib 1.5% cream, to assess the efficacy of ruxolitinib 1.5% cream in participants with AD, to understand the effect of ruxolitinib on the skin, and to provide further insight on the safety of ruxolitinib in participants with AD.

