In both studies, the majority of participants showed good local tolerability to study drug. Pooled analysis from both Phase 3 studies confirmed that the AE profile was similar to that in the vehicle group, with low rate of application site reactions and no serious AEs.

The efficacy data of these 2 Phase 3 studies revealed that either treatment regimen of ruxolitinib cream brought about rapid (within 12 hours of initiation of therapy), substantial, and sustained reduction in itch and showed superior efficacy versus vehicle in IGA-TS, $\geq 75\%$ improvement in EASI score, and ≥ 4 -point reduction in itch NRS score. Of note, numerically better results were observed in the ruxolitinib 1.5% BID group (Papp et al 2020). In addition, the Phase 2 study (INCB 18424-206) with 204 participants with AD randomized to treatment with ruxolitinib 0.15% cream QD (n = 51), ruxolitinib 0.5% cream QD (n = 51), ruxolitinib 1.5% cream QD (n = 52), or ruxolitinib 1.5% cream BID (n = 50) revealed that all ruxolitinib treatment groups were superior to the vehicle group for the percent change from baseline in EASI score at Week 4. Of note, the greatest change from baseline was measured in the ruxolitinib 1.5% cream BID group (-71.57% versus -11.90% ; $p < 0.0001$).

Given the favorable safety and efficacy profile of ruxolitinib 1.5% cream BID in participants with AD, the 1.5% concentration of ruxolitinib cream applied BID was selected to evaluate the effect of ruxolitinib cream on itch in adult participants with AD in the present study.

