6.3. Measures to Minimize Bias: Randomization and Blinding

This is an open-label study; no comparisons will be made between participants or against historical controls. Measurements of safety and efficacy are objective measurements, and only comparisons to pretreatment conditions will be made.

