5.1 Sample Size

Approximately 36 participants were planned to be enrolled into the study to receive ruxolitinib 1.5% cream. The sample size calculation was based on the CI for 1-sample mean. With an approximate 10% missing assessment rate at 24 hours, a sample size of 36 is required to produce a 2-sided 95% CI for the expected change from baseline in PP-NRS (24-hour recall period), with a precision of 0.57. The SD of 1.64 is estimated from 2 Phase 3, double-blind, randomized studies (INCB 18424-303 and INCB 18424-304). To ensure data quality and support study interpretation after deviations from protocol related to the timing of efficacy assessments were observed in the first participants enrolled, it was decided to enroll an additional 12 participants for a total of approximately 48 participants to be included.

	STATISTICAL ANALYSIS PLAN, Version Final v1.0
Protocol Number: INCB 18424-901	Sponsor: Incyte Corporation
Study Title: An Open-Label, Single-Arm Study to Evaluate the Effect of Ruxolitinib 1.5% Cream on Itch in Adult Participants With Atopic Dermatitis (SCRATCH-AD)	

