6.2 Handling of Dropouts or Missing data

No imputation will be made for efficacy data. See [Appendix 2](#) for handling of completely or partially missing dates for prior and concomitant medications and adverse events.

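### Does counting the first single score at least 2 points below baseline make the time-to-MCID analysis misleading?

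*SAP*

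**What the plan says.** SAP 12.2.3 defines time to MCID, separately for PP-NRS (in days) and mPP-NRS (in hours), as the "time from the date (time) of first dose to the date (time) of first occurrence of MCID", where MCID is a fall of at least 2 grades from baseline. SAP 12.2.5 analyses it by Kaplan-Meier and censors participants without an event at their last score. Neither document asks for a second score to confirm the first.

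The PP-NRS is "recorded daily in the eDiary from the screening visit until Day -1 and from Day 2 to the Day 29 visit", which gives 28 nominal postbaseline scores. The mPP-NRS has seven postdose scores, all on Day 1. Under SAP 6.2, "No imputation will be made for efficacy data".

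Two further parts of the plan matter here:

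- **Purpose.** Protocol 2.2.1 states: "The proposed design is considered appropriate to evaluate the onset of itch reduction following application of ruxolitinib 1.5% cream".
- **Companion output.** SAP 12.2.2 lists "Proportion of participants achieving at least a 2-grade decrease from baseline in PP-NRS from Day 2 through Day 29". SAP 12.2.5 gives these proportions Clopper-Pearson 95% intervals, does the same for mPP-NRS at each timepoint, and adds line graphs of the score and its change.

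Protocol 10.3 and SAP 5.6 rule out formal comparisons, and Protocol 6.3 says "no comparisons will be made between participants or against historical controls".

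**The concern.** A first-passage curve can only rise. Someone whose itch varies around an unchanged level may sooner or later record one score 2 points below baseline, and from then on counts as having reached MCID. With 28 looks even a small daily chance adds up, and without a control arm nothing shows how many crossings are noise. Protocol 2.2.2 describes earlier Phase 3 results as "rapid (within 12 hours of initiation of therapy), substantial, and sustained reduction in itch", so a high figure at Day 29 could be taken for lasting benefit. The apparent remedy is a second Kaplan-Meier curve that counts a crossing only if the next score also qualifies.

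At stake is how the late part of one secondary curve is read. The primary endpoint, change in PP-NRS at Day 2, does not use this definition.

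**Working it through.** **1. The plan's own figure.** SAP 5.1 gives SD 1.64, precision 0.57 and "With an approximate 10% missing assessment rate at 24 hours". Then n = (1.96 × 1.64 / 0.57)² = 31.8, rounded up to 32, and 32 / 0.90 = 35.6, rounded up to 36. The stated 36 reproduces. It concerns the primary endpoint; here it supplies only the SD of 1.64.

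**2. Direction of the effect.** If each day carries an independent chance p of a qualifying dip, P(at least one in 28) = 1 − (1 − p)^28. For p = 1%, 2%, 5% and 10% this is 24.5%, 43.2%, 76.2% and 94.8%. The accumulation is real.

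**3. Size under stated assumptions.** The documents give neither the within-person daily SD nor the day-to-day correlation, so both are assumed. The simulation uses integer scores 0-10, true mean 6, between-person SD 1.4 and lag-1 correlation 0.3. Baseline is the mean of seven run-in days, with entry at 4 or more. The individual drop is normal and complete at Day 2. Its SD (0.97 to 1.58, smaller as daily noise grows) keeps the SD of the Day 2 change near 1.64. Percentages are for daily SD 0.5 / 0.8 / 1.0 / 1.2.

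| Mean drop | First occurrence by Day 29 | Two consecutive days, by Day 29 | On any one day | Median: first / two-day |
|---|---|---|---|---|
| 1 | 52 / 67 / 77 / 87 | 42 / 51 / 57 / 65 | 29-30 | Day 21, 7, 5, 5 / not reached, Day 26, 16, 12 |
| 2 | 75 / 86 / 93 / 97 | 66 / 75 / 81 / 88 | 52-53 | Day 2 / Day 4 |
| 2.5 | 83 / 92 / 96 / 99 | 76 / 84 / 89 / 94 | 64 | Day 2 / Day 2 |

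With no effect in anyone, first occurrence by Day 3 is 0.2%, 4% and 9% at SD 0.5, 0.8 and 1.0. By Day 29 it is 2.4%, 30% and 53%. The excess builds late; the onset part of the curve is little affected.

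**4. Which output is nearest the truth?** Take mean drop 2 and SD 0.8. A separate run of this cell gives 86.7% for first occurrence, 75.2% for the two-day rule and 52.2% on any one day. The share whose true drop is at least 2 is 50.0%.

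- Excess of first occurrence: 86.7 − 50.0 = 36.7 points.
- Excess of the two-day rule: 75.2 − 50.0 = 25.2 points, so it removes (36.7 − 25.2) / 36.7 = 31% of the excess.
- Excess of the planned daily proportion: 52.2 − 50.0 = 2.2 points.

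In 48 participants that is about 41, 36 and 25 people, against 24.

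This cell favours the daily proportion, because the mean drop sits on the threshold. At mean drop 1 the true share is 1 − Φ(1/1.58) = 26% at SD 0.5 and 1 − Φ(1/0.97) = 15% at SD 1.2. The daily proportion of 29-30% then exceeds it by about 3 to 15 points, the two-day rule by 42 − 26 = 16 to 65 − 15 = 50, and first occurrence by 52 − 26 = 26 to 87 − 15 = 72. The order is unchanged.

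**5. What a confirmation rule would cost.** At mean drop 2 and SD 0.8, Day 2 attainment falls from 52% to 43%. If everyone truly drops 2 points at once, it falls from 53-56% to 36-40% and the median moves from Day 2 to Day 4. At mean drop 2, participants with a true drop below 2 make up 34-48% of first-occurrence events and still 25-43% of confirmed ones. For mPP-NRS, successive scores lie between 15 minutes and 6 hours apart. A crossing at 6 hours could be confirmed only at 12 hours, just before the evening application (Protocol Table 5). Confirmation there has no uniform meaning.

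**The case for a change.** The strongest case for the concern is that its direction follows from the definition alone and its size can be large. At mean drop 1, 52-87% would be counted by Day 29, although only 29-30% meet the threshold on any one day, and the medians differ widely between the rules. There is no control arm from which to judge the background rate. The daily proportions are cross-sectional: they do not show whether the participant who qualified on one day also qualified on the next. One supportive curve needs no new data.

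Part of this stands. The late part of the Kaplan-Meier curve is the share who have ever recorded one qualifying score, and should be read as that. The daily proportions indeed do not link days within a person. But that gap concerns durability, and a rule asking for two neighbouring scores does not measure durability either. The documents do not name the share reaching MCID by Day 29 as an endpoint of its own.

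One documentary mismatch also stands. Protocol 10.4.3 names a log-rank test for the time-to-event endpoints, SAP 12.2.5 does not carry it forward, and SAP 3.5 reports no change from the protocol. A single arm with no planned subgroups has nothing for that test to compare. Aligning the texts is clerical and alters no result.

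**Conclusion.** The concern does not hold. First occurrence is a coherent definition for an onset endpoint, and this one is secondary, descriptive and free of formal comparison. The accumulation of chance crossings is genuine but falls mainly on the late curve. The plan already reports the output that does not accumulate, day by day and with confidence intervals. At mean drop 2 and daily SD 0.8 that output lies 2.2 points from the true share, while a two-day confirmation rule lies 25.2 points away and delays the onset median by two days. Whether to add such a curve is a choice on which statisticians may reasonably differ.

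The percentages rest on an assumed daily SD (0.5 to 1.2), a correlation of 0.3, an immediate and constant drop, and the SD of 1.64 taken from other studies. The conclusion needs less: the daily proportions do not accumulate, and the endpoint is meant to date onset.

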12.2.4 Investigator's Global Assessment

The Investigator's Global Assessment (IGA) of the current state of the disease is a 5-point morphological assessment of overall disease severity.

The IGA will be analyzed as follow:

- Change from baseline in IGA at Day 8, Day 15, and Day 29.

The Investigator's Global Assessment-Treatment Success (IGA-TS) is defined as an IGA score of 0 or 1 with at least a 2-grade reduction from baseline. The IGA-TS will be analyzed as follow:

	STATISTICAL ANALYSIS PLAN, Version Final v1.0
Protocol Number: INCB 18424-901	Sponsor: Incyte Corporation
Study Title: An Open-Label, Single-Arm Study to Evaluate the Effect of Ruxolitinib 1.5% Cream on Itch in Adult Participants With Atopic Dermatitis (SCRATCH-AD)	

- Proportion of participants achieving the IGA-TS (score of 0 or 1 in IGA with at least a 2-grade reduction from baseline) at Day 8, Day 15, and Day 29.

[figure not shown]
12.2.5 Secondary Endpoints Analysis

Descriptive statistics will be presented for all secondary efficacy endpoints, by visit and timepoint (if applicable). The change from baseline and percent change from baseline in PP-NRS, mPP-NRS and IGA, and proportion endpoints for PP-NRS, mPP-NRS, and IGA-TS, will be analyzed descriptively at each visit. The 95% CI will be provided for the mean change, percent change and the proportions (using the Clopper-Pearson method). For proportion endpoints, percentages will be based on the number of participants with a response at the specified visit and timepoint.

The proportion of participants achieving an IGA score of 0 or 1 and associated 95% CI (using the Clopper-Pearson method) will also be reported descriptively.

The time to MCID will be analyzed using Kaplan Meier estimation for PP-NRS and mPP-NRS. A participant will be considered censored if he has not met the event of interest at the end of the study or if the participant is lost to follow up at last observation. Those participants will be censored at their last available mPP-NRS or PP-NRS assessment date or time. Survival curves will also be presented.

A line graph presenting the value and a line graph presenting the change from baseline in mPP-NRS over time will be produced. The value and change from baseline in PP-NRS over time and value and change from baseline in IGA will be presented similarly.

	STATISTICAL ANALYSIS PLAN, Version Final v1.0
Protocol Number: INCB 18424-901	Sponsor: Incyte Corporation
Study Title: An Open-Label, Single-Arm Study to Evaluate the Effect of Ruxolitinib 1.5% Cream on Itch in Adult Participants With Atopic Dermatitis (SCRATCH-AD)	

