6. STUDY TREATMENT

6.1. Study Treatment Administered

Ruxolitinib 1.5% cream will be supplied in 60-g tubes. The study drug will be provided by the sponsor and dispensed at the study visits summarized in the SoA (see [Table 3](#)). On Day 1, study staff will instruct participants on proper application of study drug.

All participants will apply ruxolitinib 1.5% cream for 28 (± 2) days. The study drug will be applied as a thin film, BID, on all AD lesions with a maximum treated area $\leq 20\%$ BSA. All original areas of involvement identified on Day 1 (even in the event of lesions clearing), and any new lesions (a maximum of $\leq 20\%$ BSA can be treated) must be treated until the evening prior to the Day 29 visit. The last application will be on the evening prior to the Day 29 visit. On Day 1, participants will remain at the study center until after the 6-hour mPP-NRS assessment (approximately an 8-hour stay at the site). The 12-hour mPP-NRS assessment will be done at home just prior to the evening study drug application. On Day 8 and Day 15, the morning application of the study drug will be at the study center under the supervision of study staff. Other study drug applications will be self-administered by the participants at home.

Participants will be instructed to apply the study drug at approximately the same time of the day (once in the morning and once in the evening, approximately 12 hours apart). The evening dose should be applied at least 1 hour before bedtime. On Day 1, the mPP-NRS assessments should occur as close as possible to the scheduled time relative to the first study drug application. In addition, the 12-hour mPP-NRS should be completed before the evening study drug application. On Day 2, the PP-NRS assessment should be completed approximately 24 hours after the first study drug application and before the Day 2 morning dose. Refer to [Table 5](#) for of the sequence and timing of these assessments and allowed windows on Day 1 and Day 2. From Day 3 until the Day 29 visit, the PP-NRS should be completed once daily, at approximately the same time in the morning, and prior to the study drug application.

[Table 6](#) presents the study treatment information.

Table 6: Study Treatment Information

Study treatment name:	Ruxolitinib
Mechanism of action:	JAK1 and JAK2 inhibitor
Dosage formulation:	Cream
Unit dose strength(s)/ dosage level(s):	1.5% BID

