6.5.2. Criteria for Permanent Discontinuation of Study Drug

The occurrence of unacceptable toxicity not caused by the underlying disease will require that the study drug be permanently discontinued. Unacceptable toxicity is defined as follows:

- The occurrence of an AE that is related to study treatment that, in the judgment of the investigator or the sponsor's medical monitor, compromises the participant's ability to continue study-specific procedures or is considered to not be in the participant's best interest.
- A worsening of AD that requires treatment with a prohibited concomitant medication.
- A persistent AE requiring a delay of therapy for more than 2 weeks without resolution of the AE (unless a greater delay has been approved by the sponsor).

See Section 7.1.2 for discontinuation procedures.

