6.6.3. Prohibited Medications and Procedures

[Table 8](#) lists prohibited medications that are not to be used from the defined washout periods prior to the run-in period through the last study visit.

Participants who start prohibited medications or therapies that have been demonstrated to be effective for treatment of AD/pruritus during the study will be withdrawn from the study.

Participants who start prohibited medications or therapies for other reasons during the study may be withdrawn from the study if an impact on efficacy assessment or safety of the participants is expected. If in any doubt, investigators are advised to discuss medications with the medical monitor.

Participants who present with a worsening of AD that requires treatment with a prohibited concomitant medication will have the study drug permanently discontinued.

Table 8: Prohibited Therapies or Procedures

Prohibited Medications, Products, and Procedures	Washout Period Prior to:	
	Run-In Period	Day 1
Dupilumab	26 weeks	—
Any marketed or investigational biological agent that may impact the course of AD or its assessments	12 weeks or 5 half-lives (whichever is longer)	—
Major surgery	—	8 weeks
JAK inhibitor (systemic or topical)	4 weeks	—
Nonbiological investigational product or device	4 weeks	—
Live-attenuated vaccine	4 weeks or 5 half-lives (whichever is longer)	—
Systemic corticosteroid (oral/injectable) ^a	4 weeks	—
Systemic treatment (other than biologics) that could affect AD and/or pruritus ^b	4 weeks	—
PUVA treatment, UV-B phototherapy (including tanning beds) or excimer laser, excessive sun exposure	4 weeks	—
Topical medicated treatment that could affect AD and/or pruritus ^c	2 weeks	—
Doxepin	2 weeks	—
Oral, sedative, H ₁ antihistamine ^d	2 weeks	—
Anticoagulant medication ^e	—	2 weeks
Antibiotics (systemic or topical) for infected AD	2 weeks	—

^a Intranasal corticosteroids and inhaled corticosteroids are allowed. Eye and ear drops containing corticosteroids are also allowed.

^b For example, retinoids, calcineurin inhibitors, PDE-4 inhibitors, methotrexate, cyclosporine, hydroxycarbamide (hydroxyurea), azathioprine, interferon-gamma, or opioids (agonist, partial agonist-mixed, or antagonist).

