8.7. End of Treatment and/or Early Termination

If a decision is made that the participant will permanently discontinue study drug, then the ET visit should be conducted. If the ET visit coincides with a regular study visit, the ET evaluations will supersede those of that scheduled visit, and the data should be entered in the ET visit in the eCRF. If this decision does not coincide with a regular visit, reasonable efforts should be made to have the participant return to the site to have the ET procedures completed. The participant should be encouraged to return for the follow-up visit.

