5.4 Windowing Conventions

No windowing conventions apply for this study.

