5.7 Handling of Retests, Unscheduled Visits, and Early Termination Data

When retests measurements are done, the retest measurement will be considered for the summary analysis. All data from retest visits will be listed.

Unscheduled measurements will not be summarized in by-visit summary tables or figures. However, they will be included in shift summary tables. All data from unscheduled visits will be listed.

Early Termination visit assessments will be summarized as a separate visit in by-visit outputs. All data from early termination visits will be listed.

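### IGA-TS and later PP-NRS responder rates drop participants who exit for worsening AD, so they run slightly high for the mITT set if such exits occur

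*SAP*

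**What the plan says.** SAP 12.2.5 covers IGA-TS at Days 8, 15 and 29 and the 1- and 2-grade PP-NRS reductions from Day 2 through Day 29. For these proportions, "percentages will be based on the number of participants with a response at the specified visit and timepoint". Response can only mean a recorded value here; if it meant responders, every rate would be 100%.

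Three other SAP rules bear on participants who exit:

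- Section 6.2: "No imputation will be made for efficacy data".
- Section 5.7: "Early Termination visit assessments will be summarized as a separate visit in by-visit outputs".
- Section 5.4: "No windowing conventions apply for this study", so nothing maps an ET value to a nominal day.

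Appendix 1 makes the whole analysis population the default denominator, but only where no other is specified, and 12.2.5 specifies one. The mITT set (SAP 4.3) needs a baseline and one post-baseline PP-NRS or mPP-NRS value, so a participant who exits later remains in it.

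The protocol ties treatment failure to exit. Section 6.5.2 lists as a reason for permanently stopping study drug: "A worsening of AD that requires treatment with a prohibited concomitant medication". Under Section 6.6.3, participants who start prohibited therapies "demonstrated to be effective for treatment of AD/pruritus during the study will be withdrawn from the study". Section 8.7 adds: "If the ET visit coincides with a regular study visit, the ET evaluations will supersede those of that scheduled visit", with the data entered under ET in the eCRF.

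**The concern.** The efficacy results are presented for the mITT set, but each later responder rate describes only those who still have a value at that visit. Missing values would be fairly harmless if they were unrelated to outcome. Here the protocol makes one kind of treatment failure a reason to leave, so some of the missing values belong to people who did not respond.

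For IGA there is a second route. A failing participant may be assessed on Day 8 or Day 15, but if that visit is also the ET visit, the value is filed as ET and leaves that day's IGA-TS rate although it was observed.

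There is no comparator arm that would share this selection, and the per protocol set, being a subset of mITT, cannot restore anyone. At stake is how the secondary responder rates and their intervals are read. No test, error rate or success rule depends on them.

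**Working it through.** **The plan's own figure.** The only calculated figure is the sample size for the Day 2 mean (SAP 5.1). It reproduces: (1.96 × 1.64 / 0.57)² = 31.8, rounded up to 32; 32 / 0.9 = 35.6, rounded up to 36. It concerns the primary endpoint and is not touched by this point. Its 10% missing rate applies at 24 hours only and says nothing about later exits.

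**Inputs.** N = 48, the approximate planned total (SAP 5.1), taken as the mITT size. The number of failure exits without a scheduled value, k, and the number of responders, x, are not in the documents and are assumed.

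**Formulas.**

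- Planned (observed-case) rate: x / (48 - k).
- Whole-mITT rate with the k exits as non-responders: x / 48.
- Ratio: 48 / (48 - k) = 1.021 for k = 1, 1.043 for k = 2, 1.116 for k = 5.
- Difference: x / (48 - k) - x / 48 = planned rate × k / 48.

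**Results** (Clopper-Pearson 95% CI in brackets):

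| x | k | Whole mITT | Planned rate | Shift (points) |
|---|---|---|---|---|
| 12 | 2 | 12/48 = 25.0% (13.6-39.6) | 12/46 = 26.1% (14.3-41.1) | +1.1 |
| 12 | 5 | 12/48 = 25.0% (13.6-39.6) | 12/43 = 27.9% (15.3-43.7) | +2.9 |
| 28 | 1 | 28/48 = 58.3% (43.2-72.4) | 28/47 = 59.6% (44.3-73.6) | +1.2 |
| 28 | 2 | 28/48 = 58.3% (43.2-72.4) | 28/46 = 60.9% (45.4-74.9) | +2.5 |
| 26 | 5 | 26/48 = 54.2% (39.2-68.6) | 26/43 = 60.5% (44.4-75.0) | +6.3 |

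The shift grows with the response rate. One exit at 25% gives 12/47 = 25.5%, +0.5 points; two exits at 34/48 = 70.8% give 34/46 = 73.9%, +3.1 points. The intervals in the table are 26 to 31 points wide. With k = 0 the two rates are identical.

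**Which results are exposed.**

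- IGA-TS: by both routes, exit without a later value and a Day 8 or Day 15 visit superseded by ET.
- PP-NRS responder rates: by exit only. PP-NRS is a daily eDiary entry (Protocol 8.1.4), so scores entered before exit stay in those days' rates, and the superseding rule does not clearly reach them.
- IGA 0 or 1: unclear. Its sentence in SAP 12.2.5 states no denominator, so either the observed-case rule or the Appendix 1 default could apply.
- Participants who stop drug but are still assessed, which Protocol 7.1.2 allows, keep their values in the rate.

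**The case against.** The strongest reply is that little is hidden. Protocol 10.4.1 requires sample size, frequency and percentage for categorical summaries, and SAP 7.1 reports the size of each analysis set and the discontinuation reasons. A reader can therefore divide the responders by the mITT total. Observed-case summaries are also a prespecified, open choice for a single-arm descriptive study.

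The number of exits may be very small too. Treatment lasts about 28 days, and participants with recent significant flares are excluded (Protocol 5.2). In the first part of study INCB 18424-303, atopic dermatitis was a treatment-emergent event in 1.9% (Protocol 2.2.2), which for 48 participants is 0.019 × 48 = 0.9. This is only indirect evidence: an adverse event is not an exit, and Protocol 9.1 does not record disease progression as an adverse event here.

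All of this stands as a limit on importance. It does not change what the plan reports: the printed percentage and its interval remain observed-case, and the separate ET summary does not return a superseded IGA to its day.

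A reader might infer more than the documents support:

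- *That the rates will be too high.* This follows only if failure exits occur, and no exit rate is given. Missed entries and unrelated exits bias the rates in an unknown direction.
- *That routine Day 29 IGA values are lost to ET as well.* Protocol 6.1 says otherwise: "The last application will be on the evening prior to the Day 29 visit". A participant who completes treatment has not stopped it early, so 8.7 does not apply.
- *That the primary endpoint is affected.* The point concerns responder rates; the Day 2 mean change, the Day 1 mPP-NRS results, the other mean changes and EASI-75 lie outside it.

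**Conclusion.** The mechanism is in the current text, and its effect is conditional and probably small. If k participants exit because worsening AD needs a prohibited medication and have no scheduled value at a visit, that visit's rate exceeds the whole-mITT rate, with those exits as non-responders, by 48/(48-k). For one or two exits this is a factor of 1.02 to 1.04, or about 1 to 2.5 points in the tabulated examples; five exits would give 1.12, or about 3 to 6 points.

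This rests on an mITT size of 48, on assumed values of k and of the response rate, and on treating these exits as non-responders. A wide interval reflects sampling error and does not correct a shift in one direction, so a supportive analysis is worth adding. The conduct and the primary result of the study are not in question.

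**What to change.** Amend SAP 6.2 and 12.2.5 before database lock. Keep the observed-case table and add one supportive table of IGA-TS and the PP-NRS 1- and 2-grade responder rates, plus IGA 0 or 1 with its denominator stated. In the added table:

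- The denominator is all mITT participants, and anyone without a value at the visit counts as a non-responder.
- An IGA taken at an ET visit that coincides with Day 8 or Day 15 is used as that day's value.
- Values recorded after a prohibited AD/pruritus therapy was started for worsening AD are flagged and counted as non-response. A prohibited drug taken for another condition does not trigger this.
- The Clopper-Pearson interval is given, with the number missing by reason at each visit.

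The cost is SAP wording, one derivation flag and one table. The primary discontinuation reason (Protocol 7.1.2) and concomitant medications (Protocol 6.6) are already in the eCRF. Deciding whether a therapy was started for worsening AD needs some judgement, so it should be settled before lock, when protocol deviations are classified anyway (SAP 7.2).

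The drawback is a slightly lower, conservative rate, because unrelated missing values also count as non-response. The observed-case table beside it shows the less strict reading.
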